**4.2.3 Follow Up Phase**

**Visit 5 (Group 2: Visit 1 + 41-43 days)**

**The following tasks will be performed**

- Blood draw (serum collection) for antibody analysis (16 ml)

**Visit 6 (Group 2: Visit 1 + 55-57 days)**

**The following tasks will be performed**

- Blood draw (serum collection) for antibody analysis (16 ml)

To monitor long-term safety, the clinical trial site will contact the subjects by remote correspondence (e.g. telephone or email) 6 months after the last trial vaccination to inquire whether SAEs and/or AESIs might have occurred since the last trial visit. In cases where a serious condition is detected, the trial subject will be asked to return for a physical examination and further work-up at the clinical trial site or (specifically in the case of deployed military subjects) at another medical unit as agreed upon by the Principal Investigator (PI).

#### **Remote FU (Last vaccination + 182 – 210 days)**

The following tasks will be performed:

- FU on ongoing AEs, AESIs, SAEs and recording of new SAEs/AESIs

In case a physical visit is deemed necessary, the following should be performed:

- Targeted physical examination, including auscultation of heart and lungs; see [Section 8.2.3](#) for more details
- Review of prior / concomitant medications, (if related to an ongoing AE, AESIs, SAEs and new SAEs/AESIs)
- Blood draw (10 ml) for safety laboratory (CBC with differential, total bilirubin, Alk Phos, AST, ALT, creatinine, sodium, potassium and calcium, if clinically indicated)
- Other safety evaluation, if clinically indicated

#### **4.2.4 Unscheduled Visits**

If clinically indicated, additional visits may be necessary between scheduled visits. Unscheduled visits may be performed to repeat laboratory testing or physical exams due to a new development. Unscheduled visits may occur when subjects request assistance with or experience problems with bandage changes after ACAM2000® vaccination. In cases where the vaccination site has not fully healed at Visit 4 in Group 2 subjects and at Visit 10 in Group 1 subjects, then the subject would be asked to provide date that scab fell off. Examinations, performed at unscheduled visits will be documented in the source documents as well as on the respective CRF pages for unscheduled visits.

#### **4.2.5 Withdrawal from Further Trial Vaccinations (Group 1)**

The decision not to administer further trial vaccinations can be made by the PI as well as by the subject.

Criteria:

For Group 1 subjects the following criteria should be checked prior to administration of the second MVA-BN® vaccination at Visit 4 and the ACAM2000® vaccination at Visit 7.

If any are applicable, the subject should not receive any of these vaccinations:

- Any clinically significant cardiac sign and symptom.

The detection of cardiac events indicative for cases of myo-/pericarditis are collected as AESI, defined as:

- Any cardiac sign or symptom (e.g. chest pain, shortness of breath etc.) developed since the first vaccination
- ECG abnormalities determined to be clinically significant by the investigating physician
- Cardiac enzyme troponin I  $\geq 2 \times$  ULN ( $\geq$  Grade 2 according to the toxicity scale provided in [Appendix I; Section 17.1](#))

Case definitions for acute myocarditis and pericarditis, as published by the Center of Disease Control and Prevention (CDC) ([MMWR, May 30, 2003](#)) are provided in [Appendix III; Section 17.3](#), in order to:

- help Investigators to recognize possible events of acute myocarditis and/or pericarditis and
  - distinguish from unspecific and isolated ECG abnormalities without or with unclear clinical significance.
- An AE that, in the opinion of the investigator, makes it unsafe for the subject to receive any further trial vaccination. In this case, the appropriate measures will be taken
  - Anaphylactic reaction following the administration of any vaccine(s)
  - Start of chronic administration (defined as more than 14 days) of  $> 5$  mg prednisone (or equivalent) per day or any other immune-modifying drugs
  - Administration of immunoglobulins and/or any blood products
  - Clinical need for concomitant or ancillary therapy not permitted in the trial
  - Use of any investigational or non-registered drug or vaccine other than the trial vaccine
  - Any condition which contradicts administration of any further trial vaccination in the opinion of the investigator
  - Pregnancy
  - Subject refuses to receive any further vaccination

Procedure:

If the subject is withdrawn from further trial vaccinations the reason for this decision should be recorded. The procedures below should be followed:

If withdrawn after the 1st MVA-BN® vaccination

- All visits up to Visit 4 must be performed according to the trial procedure schedule.
- Visit 5 to Visit 10 will not be performed.
- The remote FU Visit has to be performed 182 to 210 days after Visit 1.

If withdrawn after the 2nd MVA-BN® vaccination

- All visits up to Visit 7 must be performed according to the trial procedure schedule
- Visit 8 to Visit 10 will not be performed
- The remote FU Visit has to be performed 182 to 210 days after Visit 4

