### Screening Visit (Days -70 to -1)

The following tasks will be performed:

- Subject to read, sign and date Informed Consent Document (ICD)
- Check inclusion/exclusion criteria (which incorporates the criteria from the US Department of Defense [DoD] Smallpox Vaccine Screening Forms)
- Obtain medical/surgical history
- Check vaccination history and absence of smallpox vaccine scar
- Complete physical examination / vital signs (temperature, pulse, respiratory rate and blood pressure, including auscultation of heart and lungs and measurement of body weight and height and examination of axillary and supraclavicular lymph nodes)
- Evaluation of vital signs, BMI calculation and calculation for creatinine clearance
- Recording of baseline signs and symptoms
- Check cardiac risk factors, including immediate family (father, mother, brother or sister) risk factors, total cholesterol, high-density and low-density lipoprotein (HDL, LDL) and calculation of individual cardiac risk factor
- Perform baseline ECG
- Review of prior/concomitant medications
- Counseling on avoidance of contact spread (specifically after ACAM2000® vaccination), HIV infection, and pregnancy: Review of acceptable contraceptive methods and recent menstrual history with WOCBP.
- Blood draw (22 ml) for safety laboratory (CBC with differential, total bilirubin, Alk Phos, AST, ALT, creatinine, sodium, potassium and calcium) including total, HDL and LDL cholesterol, hepatitis serology (HBsAg, Anti-HCV), HIV, troponin I and serum pregnancy test

If a subject is screened and cannot be vaccinated because of a certain transient condition (e.g. abnormal lab value due to an acute condition or a missing lab evaluation due to mishandling of the sample), then the subject can be re-screened on one further occasion only and the respective tests should be repeated as a "partial" re-screening rather than a "full" re-screening. The re-screening visit must be within the 70 day window started by the first Screening Visit and the window -70 to 1 day before 1st vaccination must not be exceeded. A "partial" re-screening visit is indicated by completing only the respective re-screening sections of the Case Report Form (CRF).

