### Visit 1 (Day 0)

Tasks to be performed prior to randomization and vaccination:

- Re-check inclusion/exclusion criteria
- Check of safety laboratory results obtained at Screening Visit
- Targeted physical examination, including auscultation of heart and lungs, see [Section 8.2.3](#) for more details
- Evaluation of vital signs
- Recording of baseline signs and symptoms
- Questions on cardiac signs and symptoms
- Review of prior/concomitant medications
- Assessment of axillary and supraclavicular lymphadenopathy, see [Section 8.2.3](#) for more details
- Examination of the possible deltoid vaccination sites
- Counseling on avoidance of contact spread (specifically after ACAM2000® vaccination), HIV infection and pregnancy
- Urine or serum pregnancy test (5 ml, if applicable)
- Blood draw (serum collection) for antibody analysis (16 ml)

Blood draws and all other tasks mentioned above must always be performed prior to vaccination. If the subject is still eligible for participation in this trial, the subject will be randomized. The following tasks will be performed after randomization:

- Vaccination: Group 1: administration of one (1) dose of MVA-BN®  
Group 2: administration of one (1) dose of ACAM2000®
- Subject observation by clinical trial site staff for at least 30 minutes after vaccination

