**Visit 7 (Visit 1 + 55-57 days)**

The following tasks will be performed

- Targeted physical examination, including auscultation of heart and lungs; see [Section 8.2.3](#) for more details
- Evaluation of vital signs
- Questions on cardiac signs and symptoms
- Review of prior/concomitant medications
- Counseling on avoidance of contact spread, HIV infection and pregnancy
- Examination of vaccination site
- Assessment of axillary and supraclavicular lymphadenopathy, see [Section 8.2.3](#) for more details
- Recording of AEs/SAEs/AESIs
- Urine or serum pregnancy test (5 ml, if applicable)
- Blood draw (serum collection) for antibody analysis (16 ml)
- Check of safety laboratory results obtained at Visit 6

Tasks mentioned above must always be performed prior to vaccination.

- Administration of one dose of ACAM2000®

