### **5.3 Exclusion Criteria**

1. Pregnant or breast-feeding women
2. Typical vaccinia scar
3. Known or suspected history of smallpox vaccination defined as visible vaccination scar or documentation of smallpox vaccination or as reported by the subject
4. History of vaccination with any poxvirus-based vaccine
5. History of any serious medical condition, which in the opinion of the investigator would compromise the safety of the subject
6. History of or active immunodeficiency or immunosuppression caused by acquired or congenital diseases or caused by ongoing treatments such as chronic (> 14 days) high-dose corticosteroids (> 5 mg prednisone [or equivalent] per day applied systemically, i.e. parenterally or orally), chronic or planned treatment with steroid eye drops or ointment at time of screening or radiation, or immunosuppressive drugs; low-dose corticosteroid topical products and nasal sprays used sporadically, i.e. pro re nata are permissible
7. Having had radiation or X-ray treatment (not routine X-rays) within the last 3 months
8. Post organ and bone-marrow transplant subjects whether or not receiving chronic immunosuppressive therapy
9. Recent surgery (including dental or eye) within 4 weeks prior to trial vaccination
10. History of or active autoimmune disease. Persons with vitiligo or thyroid disease taking thyroid hormone replacement are not excluded
11. Uncontrolled serious infection, i.e. not responding to antimicrobial therapy
12. History of malignancy, other than squamous cell or basal cell skin cancer, unless there has been surgical excision considered to have achieved cure. Subjects with history of skin cancer must not be vaccinated at the previous site of cancer

13. History of keloid formation
14. History or clinical manifestation of severe hematological, renal, hepatic, pulmonary, central nervous, cardiovascular or gastrointestinal disorders
15. History of coronary heart disease, myocardial infarction, angina, congestive heart failure, cardiomyopathy, stroke or transient ischemic attack, uncontrolled high blood pressure, significant arrhythmia with or without corrective/ablative surgery, or any other heart condition under the care of a doctor
16. Chest pain (that is diagnosed as cardiac related) or trouble breathing on exertion

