17. Ten percent or greater risk of developing a myocardial infarction or coronary death within the next 10 years, e.g. using the National Heart, Lung and Blood Institute's Risk Assessment Tool: <http://cvdrisk.nhlbi.nih.gov/calculator.asp>  
NOTE: This criterion applies only to subjects 20 years of age and older
18. History of an immediate family member (father, mother, brother, or sister) who has had onset of ischemic heart disease before the age of 50 years
19. Clinically significant psychological disorder not adequately controlled by medical treatment
20. Active or history of chronic alcohol abuse and/or intravenous and/or nasal drug abuse (within the past 6 months)
21. History of anaphylaxis or any severe allergic reaction or serious adverse reaction to a vaccine
22. Eczema of any degree or history of eczema
23. People with active AD (characterized by pruritus, eczematous lesions, xerosis (dry skin), and lichenification (thickening of the skin and an increase in skin markings) or with a history of AD
24. People with chronic exfoliative skin disorders/conditions
25. People with active current Varicella zoster, Herpes zoster, impetigo, uncontrolled acne, Darier's disease, recent tattoos or skin piercing (until it is healed, but not within 4 weeks prior to trial vaccination), or any acute skin disorders of large magnitude, e.g., laceration requiring sutures
26. People with a tattoo that covers the vaccination injection area (preventing assessment of the area and interfering with a vaccination take assessment photograph)
27. Having received any vaccinations or planned vaccinations with a live vaccine (except trial vaccine) within 28 days prior to or after trial vaccination
28. Having received any vaccinations or planned vaccinations with a killed vaccine within 14 days prior to or after trial vaccination

29. Administration or planned administration of immunoglobulins and/or any blood products during a period starting from three months prior to administration of the vaccine and ending at trial conclusion
30. Use of any investigational or non-registered drug or vaccine other than the trial vaccines within 28 days preceding the first dose of the trial vaccine or planned administration of such a drug /vaccine during the trial period
31. Blood donation for the duration of the trial
32. Acute disease (illness with or without a fever)
33. Temperature  $\geq 100.4^{\circ}\text{F}$  ( $38.0^{\circ}\text{C}$ )

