34. Known household contacts with, or occupational exposure to (other than minimal contact) any of the following:
  - Pregnant women
  - Children <12 months of age
  - People with eczema or a history of eczema
  - People with active AD or history of AD
  - People with chronic exfoliative skin disorders/conditions
  - People with active Varicella zoster, Herpes zoster, impetigo, uncontrolled acne, Darier's disease or any acute skin disorders of large magnitude, e.g., laceration requiring sutures, burn greater than 2×2 cm
  - People with active or recent immunodeficiency disease or use of immunosuppressive medications, for example: have or take medication for HIV, AIDS, leukemia, lymphoma, or chronic liver problem, have or take medication for Crohn's disease, lupus, arthritis, or other immune disease; have had radiation or X-ray treatment (not routine X-rays) within the last 3 months; have ever had a bone-marrow or organ transplant (or take medication for that); or have another problem that requires steroids, prednisone or a cancer drug for treatment
  - People having had eye surgery within the last 4 weeks
35. Known allergy to MVA-BN® vaccine or any of its constituents, e.g. tris(hydroxymethyl)-amino methane, including known allergy to egg or aminoglycoside (gentamycin)
36. Known allergies to ACAM2000® and its diluents including polymyxin B sulfate, neomycin sulfate, and phenol
37. Known allergies to VIG including thimerosal or previous allergic reaction to immunoglobulins
38. Known allergies to cidofovir, sulfa drugs, Tecovirimat (ST246) or probenecid
39. Trial personnel

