### **8.3.3 Reporting of Pregnancy**

If a subject becomes pregnant during the active trial period (up to and including one month [minimum 28 days] after receiving a dose of vaccine) this pregnancy must be reported to BN on a Pregnancy Report Form within 24 hours of the investigator's becoming aware of the event. If ACAM2000® is administered during pregnancy or if the vaccinee lives in the same household with or has close contact with a pregnant woman the vaccinee should be apprised of the potential hazard to the fetus. These cases will be reported to the OHU&E and/or HQ USAMRMC IRB as appropriate.

A reportable pregnancy should be followed to term, any premature terminations reported, and the health status of the mother and child including date of delivery and the child's gender and weight should be reported to BN as soon as possible after delivery.

Any event during pregnancy fulfilling the criteria for an SAE will be reported as SAE to BN PV. However, hospitalization for delivery is a prospectively planned hospitalization and is not considered a SAE per se.

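### The trial's own procedures record no re-check of at-risk household or occupational contacts (exclusion 34) before Group 1 receives ACAM2000 at Day 56

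*Protocol*

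**What the plan says.** Exclusion 34 (Protocol 5.3) bars anyone with "Known household contacts with, or occupational exposure to (other than minimal contact) any of the following", followed by eight categories, among them pregnant women, infants under one year, people with eczema or atopic dermatitis, and people with immune deficiency. Two other exclusions look back four weeks from a dose: no. 9, "Recent surgery (including dental or eye) within 4 weeks prior to trial vaccination", and no. 25, "recent tattoos or skin piercing (until it is healed, but not within 4 weeks prior to trial vaccination".

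The eligibility check appears at two visits. At screening (4.2.1) the task is "Check inclusion/exclusion criteria (which incorporates the criteria from the US Department of Defense [DoD] Smallpox Vaccine Screening Forms"; at Visit 1 (4.2.2) it is "Re-check inclusion/exclusion criteria". The Group 1 schedules in Protocol 1.5 and SAP Table 1 mark it at those two visits only.

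At Visit 7, on contacts, the task list has "Counseling on avoidance of contact spread, HIV infection and pregnancy". Section 4.2.5 opens its list with "For Group 1 subjects the following criteria should be checked prior to administration of the second" MVA-BN dose at Visit 4 and the ACAM2000 dose at Visit 7. Section 8.3.3 adds that "if the vaccinee lives in the same household with or has close contact with a pregnant woman the vaccinee should be apprised" of the hazard to the fetus.

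**The concern.** Exclusion 34 protects people who have not consented to the trial from transmissible vaccinia. In Group 1 it is answered before MVA-BN, which Protocol 2.9.1 describes as replication incompetent, and the answer is then carried forward about eight weeks to the live vaccine for which it matters most. A partner's pregnancy, a newborn, or a housemate starting immunosuppressive treatment could arise in between, and the trial procedures as written could be followed exactly without anyone asking.

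The protocol treats comparable facts differently. It repeats the whole eligibility check at Visit 1 although screening is at most 70 days old, and it re-tests the subject's own pregnancy before every vaccination. Section 8.3.3 expects a vaccinee close to a pregnant woman to be warned, but no Visit 7 question would reveal her.

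The appended prescribing information (Appendix IVc) records deaths among accidentally infected contacts (label 5.1) and suggests that better screening, together with bandaging, explains the lower rate of preventable events in recent programs (label 5.1.2).

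**Working it through.** **Inputs.** Protocol 1.5, 4.2.1, 4.2.2, 4.2.5, 5.3, 6.2, 8.3.3 and 9.4; Appendices IVc and IVd; SAP Table 1, 3.6 and 3.7.2.

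**1. What is asked before ACAM2000**

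| | Group 2 | Group 1 |
|---|---|---|
| Day of ACAM2000 | Visit 1, Day 0 | Visit 7, Day 55–57 |
| Age of last full eligibility check | 0 days | 55–57 days |
| Vaccine given at that check | ACAM2000 | MVA-BN |

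The Visit 7 pre-vaccination tasks are targeted examination, vital signs, cardiac questions, medication review, counseling, vaccination-site and lymph-node examination, adverse events, pregnancy test, antibody sample and review of Visit 6 laboratory results. The 4.2.5 list covers cardiac findings, adverse events, anaphylaxis, steroids and immune-modifying drugs, immunoglobulins and blood products, non-permitted therapy, other investigational products, the investigator's opinion, pregnancy and refusal. Of the eight categories in exclusion 34, neither list asks about any.

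**2. Secondary point: the four-week look-backs.** A 28-day window before Day 55–57 opens on Day 55 − 28 = 27 to Day 57 − 28 = 29. The Visit 1 answer precedes that opening by 27 to 29 days and covers none of the 28 days.

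**3. What the appendices add.** The DoD form in Appendix IVd asks about recent surgery (item 8), household pregnancy (9), a child under one year (10), skin problems including tattoo and piercing in self or contact (15), immune problems in self or contact (16a), and eczema or atopic dermatitis in self or contact (17a). Its contact items concern people the subject lives with. They do not reach occupational exposure or a contact's eye surgery, and the surgery, tattoo and piercing items carry no four-week window.

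**4. Scale.** The documents give no rate at which at-risk contacts newly arise, so missed cases cannot be counted. For orientation only, label Table 2 reports 52 contact transmissions in 730,580 DoD vaccinations:

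52 / 730,580 = 71.2 per million (exact Poisson 95% CI 53.2 to 93.3)

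71.2 per million × 220 = 0.016 per 220 vaccinees (0.012 to 0.021).

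This comes from Dryvax in a screened program. It does not measure the effect of leaving out a question.

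**5. Cost in power.** A Group 1 subject whose ACAM2000 is withheld leaves the Per Protocol Set (SAP 3.7.2, item 4). The allowance gives 220 × 0.80 = 176 against 175 required. PRNT non-inferiority power uses a noncentral t with noncentrality 0.301 / [SD × √(1/n₁ + 1/n₂)], n₁ + n₂ − 2 degrees of freedom, one-sided 2.5% and true difference zero. It first reproduces the plan's 90.0% at 175 per group with SD 0.866. The losses of 5 and 10 are assumptions.

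| Group 1 / Group 2 | SD 0.866 | SD 0.807 |
|---|---|---|
| 176 / 176 | 90.2% | 93.7% |
| 171 / 176 (5 lost) | 89.8% | 93.4% |
| 166 / 176 (10 lost) | 89.3% | 93.0% |

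SAP Table 5 gives the lesion-area endpoint 99.8% power at 150 per group, so these losses do not threaten it.

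**The case against.** The strongest reply is that screening at the ACAM2000 dose is the military clinic's job. Protocol 4.2.2 makes that clinic responsible for giving the vaccine; 6.2 and 6.2.1 place it under DoD guidance and refer to the appended label for administration. Label 5.10 says that susceptible people are to be identified and kept from contact with active lesions, and label 17.2 requires vaccinees to be told to avoid them. The DoD form is worded for completion before smallpox vaccination, which describes a Group 1 subject at Day 56. The policy memorandum in Appendix IV is blacked out and may require the form for every recipient.

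This largely stands as a limit on the claim. A reader might infer that Group 1 receives live vaccinia with no contact screening at all. The documents do not support that: a clinic re-screen may well happen, and text that is blacked out cannot be counted as absent. What remains is that no readable text places the question at Visit 7 or in a trial record, and the one readable place where the DoD criteria are applied is the eligibility check at screening. Counseling may prompt a disclosure, but it is not a recorded question with a consequence. Investigator discretion cannot act on a contact nobody has mentioned.

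Two further objections are fair. Exclusions 9 and 25 are worded relative to trial vaccination and so can be read as covering each dose; surgery or a tattoo may also surface through examination, adverse-event recording or medication review. That limb is secondary. And Protocol 2.6.2 and 2.7 report that MVA-BN priming reduced viral replication at the Dryvax site and sped healing, so Group 1 may be less infectious than the population behind the 71 per million.

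**Conclusion.** The point holds as a gap in the trial's own schedule, Visit 7 tasks and 4.2.5: no recorded re-check of exclusion 34 precedes ACAM2000 in Group 1, and the last scheduled one is 55 to 57 days old. It is a low-frequency, third-party safety improvement worth making because the possible harm is serious and the check is cheap.

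It should not be stretched. A reader might infer that the subject's own new skin disease or ocular steroid use would also slip through; those are largely reachable through examination, medication review, adverse-event recording and the open items in 4.2.5. Nor does it bear on either co-primary endpoint or any analysis. The conclusion assumes only that the readable text is what governs the trial record. If the blacked-out memorandum requires the form for each ACAM2000 recipient, the gap shrinks to a missing cross-reference. Confidence is moderate for that reason.

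**What to change.** - Add to the Visit 7 pre-vaccination tasks, and to the Group 1 schedules in the protocol and SAP, a recorded repeat of the Appendix IVd screening form. Supplement it with questions on occupational exposure and a contact's eye surgery, and on the subject's surgery, tattoo or piercing in the previous four weeks.
- Add to 4.2.5 a criterion that applies to ACAM2000 only: withhold the dose if an exclusion 34 contact is present and contact cannot be avoided. It must not sit in the common list, which would also block the second MVA-BN dose at Visit 4. Deferral has little use here: the Visit 7 window spans 57 − 55 = 2 days, enough only for a condition about to resolve and not for a household pregnancy, infant or eczema contact.
- If the memorandum already requires the form for each ACAM2000 recipient, a cross-reference at Visit 7 and a CRF field for the form's date are enough.

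The cost is protocol wording, a few minutes per Group 1 subject at an existing visit, and an occasional loss from the Per Protocol Set.
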